### **8.6. Vital Signs**

Vital signs including blood pressure, heart rate, temperature, and respiratory rate will be measured at the times specified in the Schedule of Events ([Appendix A](#), [Appendix B](#) and [Appendix C](#)).

### **8.7. Physical Examination, Weight and Height**

Physical examination, height (screening only) and weight must be performed as indicated in the Schedule of Events ([Appendix A](#), [Appendix B](#) and [Appendix C](#)). A complete physical examination including assessments of general appearance, skin, head (eyes, ears, nose, and throat), neck, lungs, heart, abdomen, back, lymph nodes, extremities, and neurological system will be

completed at screening and EOT. Directed physical examinations will be completed at additional time points as specified in the Schedule of Events.

## **8.8. Assessment of Health-related Quality of Life**

In Part 2 and Part 3 of the study, HRQoL will be assessed at Day 1 of each cycle (before Debio 1562 infusion), at the EOT visit and at the 30-day safety follow-up visit ([Appendix B](#) and [Appendix C](#)). The FACT-Lym instrument will be used and will be self-administered via pen and paper. The FACT-Lym is a standardized measure of HRQoL specific to patients with NHL. It is comprised of the Functional Assessment of Cancer Therapy-General version 4 (27 items), scored in four domains (Physical well-being: 7 items; Social/Family well-being: 7 items; Emotional well-being: 6 items; Functional well-being: 7 items), and the FACT-Lymphoma Subscale, reflecting Lymphoma specific concerns (15 items).

In patients who exceptionally continue the study treatment beyond Cycle 6, the last HRQoL assessment will be performed at C7D1 before infusion instead of at EOT visit, and no additional HRQoL assessment will be completed at the 30-day follow-up visit.

## **8.9. Electrocardiogram (ECG)**

A standard 12-lead ECG will be performed as outlined in the Schedules of Events ([Appendix A](#), [Appendix B](#) and [Appendix C](#)).

## **8.10. Laboratory Assessments**

Laboratory assessments will be performed as outlined in the Schedules of Events ([Appendix A](#), [Appendix B](#) and [Appendix C](#)) and as clinically indicated.

Note that prior to each administration of Debio 1562, laboratory results must be reviewed to evaluate for potential toxicity.

Clinical laboratory tests will include the following:

### **8.10.1. Hematology**

- Hematocrit (Hct)
- Hemoglobin (Hgb)
- Platelet count
- Red blood cell (RBC) count
- WBC count with differential

### **8.10.2. Serum Chemistry**

- Albumin (ALB)
- Alkaline phosphatase (ALK-P)
- ALT; SGPT
- AST; SGOT
- Lactate dehydrogenase (LDH)
- Magnesium
- Phosphorus
- Potassium (K)

- Blood urea nitrogen (BUN)
- Calcium (Ca)
- Chloride (Cl)
- Creatinine
- Glucose
- Sodium (Na)
- Total bilirubin
- Total protein
- Uric acid
- Immunoglobulin levels (IgG, IgA, IgM)

#### **8.10.3. Urinalysis**

- Appearance, specific gravity and pH
- Semi-quantitative dipstick evaluation of glucose, protein, bilirubin, ketones, leukocytes and blood
- Microscopic examination of sediment to be performed if urinalysis is positive for WBC, proteins or blood

#### **8.10.4. Coagulation**

- Prothrombin time (PT) or INR
- Activated partial thromboplastin time (aPTT)

#### **8.10.5. Viral Serology**

Patients will be tested during screening for HBsAg.

### **8.11. Pregnancy Screen**

All female patients of child-bearing potential will complete a serum beta-human chorionic gonadotropin ( $\beta$ -hCG) or urine pregnancy test (as Institutional or Country requirements dictate) during screening and at time points specified in the Schedules of Events ([Appendix A](#), [Appendix B](#) and [Appendix C](#)). The Sponsor will notify investigators where country-specific pregnancy testing requirements are requested by the National Health Authority. If the test is performed within three days prior to start of study treatment, it need not be repeated on Day 1 of Cycle 1. The pregnancy test result must be negative for the patient to be enrolled and to receive the study drug.

If a female patient becomes pregnant while participating in this study, the Investigator and Sponsor must be informed immediately and the patient will be withdrawn from study treatment if the pregnancy is confirmed ([Section 9.2.2](#)).

Female patients who are not of childbearing potential are defined those meeting at least one of the following criteria:

1. Have undergone a documented hysterectomy and/or bilateral oophorectomy;
2. Have medically-confirmed ovarian failure;
3. Achieved postmenopausal status, defined as follows: cessation of regular menses for at least 12 consecutive months with no alternative pathological or physiological cause;

status may be confirmed by having a serum follicle stimulating hormone level within the laboratory's reference range for postmenopausal women.

### **8.12. B-symptom assessment**

B-symptoms (unexplained fevers [body temperature of  $> 38^{\circ}$  Celsius], drenching night sweats and/or weight loss greater than 10% of body weight) will be documented at time points specified in the Schedule of Events ([Appendix A](#), [Appendix B](#) and [Appendix C](#)).

### **8.13. Eastern Cooperative Oncology Group Performance Status**

ECOG performance status ([Appendix H](#)) will be assessed during screening and at other times specified in the Schedule of Events ([Appendix A](#), [Appendix B](#) and [Appendix C](#)). An assessment is not necessary on Day 1 of Cycle 1 if the screening assessment was obtained within three days prior to Day 1.

### **8.14. Radiologic Imaging and Tumor Response Assessment**

Tumor response assessment will be based on the 5-point scale per the Lugano classification of response assessments of Hodgkin and NHL ([Cheson 2014](#)).

Radiographic tumor evaluation by computed tomography (CT) or positron-emission tomography (PET)-CT scan of chest, neck, abdomen, and pelvis will be performed within 28 days prior to first dose of study treatment. The anatomical regions to be assessed radiographically post baseline will be determined individually by extent of disease. Though less preferred, a MRI is acceptable. Patients with FDG-avid disease will be followed by [ $^{18}\text{F}$ ]-FDG-PET scan. Repeat assessments will be performed every 6 weeks  $\pm$  1 week, beginning at Cycle 1, Day 1 and will not shift as a result of delays in study treatment.

Whenever possible, the same radiographic scan assessment used at screening (e.g., PET-CT) should be used at all subsequent radiographic evaluations.

**Response Follow-up:** Patients who have discontinued study treatment for reasons other than PD will be followed by radiographic assessment every 12 weeks ( $\pm$  4 weeks), beginning from the time of the patient's last on-study tumor assessment, until documentation of PD, or beginning subsequent anti-cancer therapy or death.

For patients who are exceptionally granted continued study treatment after completion of 6 cycles, repeat radiographic tumor response assessments can be performed as per local institutional care practice. Ideally, repeat assessments should continue at 6-week ( $\pm$  1 week) intervals and should not be longer than 12-weeks ( $\pm$  4 weeks). Periodic tumor assessment will be conducted using the same imaging modality of prior cycles of treatment until PD, start of any new anti-cancer therapy, or death.

### **8.15. Bone Marrow Assessment**

If applicable, a bone marrow assessment will be performed within three months prior to the first dose. A repeat bone marrow biopsy or aspirate will be required for patients with bone marrow infiltration at baseline who have a CR by imaging and physical examination and will, in case possible and deemed acceptable by the Investigator, be performed every 6 weeks as clinically

indicated. In order to better understand the effect of Debio 1562 on WBCs, bone marrow biopsies/aspirates may also be requested for those patients who experience Grade 4 cytopenias.

### **8.16. Tumor Biopsy**

Patients must provide a fresh or archived tumor biopsy sample reflecting their DLBCL disease. If the tissue biopsy is older than 18 months and a fresh one cannot be available, patient should provide FNA samples as described in the lab manual. De-identified pathology reports should be included with sample shipment to the Sponsor or designee. Addendums to pathology reports should be shared with the Sponsor or designee as soon as they are available. If a patient has a tumor biopsy obtained any time while on study, slides may be requested to be sent to the Sponsor for further [REDACTED] testing or testing for the presence of Debio 1562 or DM-1 in the sample; the pathology report for such a sample should also be shared with the Sponsor. If there is no medical urgency, the timing of the biopsy or surgical operation relative to the administration of Debio 1562 and the nature of the sample to be given to the Sponsor should be coordinated with the Sponsor, in order to enable observation of the drug and/or its components in the tumor. Pathology reports performed on older biopsies of the patient should be shared with the Sponsor or designee when available.

Details of sample preparation and shipping of tumor biopsies are described in the Laboratory Manual.

[REDACTED]

[REDACTED]

[REDACTED]

[REDACTED]

[REDACTED]

## 9. ASSESSMENT OF SAFETY

### 9.1. Recording Adverse Events and Serious Adverse Events

AEs (including SAEs) will be documented on the AE eCRF and monitored continuously throughout the study from the time informed consent is obtained until 30 days after the patient's last study treatment or until the event has resolved or stabilized or an outcome has been reached, whichever comes first.

For patients who discontinue study treatment due to a study-related AE, the reporting time-period may be extended. These patients must be followed at least once a week for four weeks, and subsequently at 4-week intervals until resolution or stabilization of the AE or laboratory abnormality, whichever comes first ([Section 5.10.1](#)).

If the Investigator considers it necessary to report an AE considered study drug related in a patient occurring after the end of study, he or she should contact the Sponsor to determine how the AE should be documented and reported.

#### 9.1.1. Definition of Adverse Events

##### 9.1.1.1. Adverse Event (AE)

An AE is any noxious, pathologic, or unintended change in anatomical, physiologic, or metabolic function as indicated by physical signs, symptoms, or laboratory changes occurring in any phase of a clinical study, whether or not considered study drug-related. This includes an exacerbation of a pre-existing condition. AEs include:

- Worsening (change in nature, severity, or frequency) of conditions present at the onset of the study
- Intercurrent illnesses
- Drug interactions
- Events related to or possibly related to concomitant medications
- Abnormal laboratory values (this includes significant shifts from baseline within the range of normal that the Investigator considers to be clinically important)
- Clinically significant abnormalities in physical examination, vital signs, and weight

Note that PD should not be reported as an AE.

Throughout the study, the Investigator must record all AEs which occur in a patient from the time that informed consent is obtained until 30 days after last study treatment on the AE CRF, regardless of the severity or relationship to study drug. The Investigator should treat patients with AEs appropriately and observe them at suitable intervals until the events stabilize or resolve. AEs may be discovered through observation or examination of the patient, questioning of the patient, complaint by the patient, or by abnormal clinical laboratory values.

In addition, AEs may also include laboratory values that become significantly out of range. Such abnormal laboratory values or test results constitute AEs if they induce clinical signs or symptoms, i.e., are considered clinically significant (e.g., a clinically significant AE resulting in study

discontinuation constitutes in and of itself an SAE), or require therapy (e.g., any hematologic abnormality that requires transfusion or granulocyte growth factor treatment); and should be recorded on the AE eCRF under the signs, symptoms or diagnosis associated with them. For abnormal laboratory values that qualify as a DME, patients must have an evaluation within 48-72 hours, and then followed until return to baseline or stabilization, whichever comes first.

An AE will be considered to be a TEAE if it begins or worsens on or after the first dose of Debio 1562 or rituximab, whichever occurs first, and before the 30-day following the last dose of Debio 1562 or rituximab, whichever occurs last.

#### **9.1.1.2. Serious Adverse Event (SAE)**

A SAE is any AE occurring at any dose that results in any of the following outcomes:

- Death
- Is life-threatening
- Requires inpatient hospitalization
- Requires prolongation of existing hospitalization
- A persistent or significant disability or incapacity or substantial disruption of the ability to conduct normal life functions
- A congenital anomaly or birth defect
- Important medical events that may not result in death, be life-threatening, or require hospitalization may be considered an SAE when, based upon appropriate medical judgment, they may jeopardize the patient and may require medical or surgical intervention to prevent one of the outcomes listed in this definition. Examples of such medical events include allergic bronchospasm requiring intensive treatment in an emergency room or at home, blood dyscrasias or convulsions that do not result in inpatient hospitalization.

Note that hospitalization is defined as admission to treat a clinical AE. The following events would not be considered hospitalizations for SAE reporting purposes: 23-hour hold for observation, admission to a hospice facility or nursing home, respite care, outpatient surgery, social admission (e.g. a patient who has nowhere to sleep) or admission not associated with a precipitating clinical AE (e.g. elective or pre-planned surgery, or in-patient administration of subsequent chemotherapy, etc.).

All AEs will be evaluated according to version 4.03 of NCI CTCAE. If the AE is not listed in the CTCAE version 4.03, it should be graded for severity based on the description given in [Table 7](#).

**Table 7: Adverse Event Severity**

Severity	Definition
Grade 1 (Mild)	No limitation of usual activities.
Grade 2 (Moderate)	Some limitation of usual activities.
Grade 3 (Severe)	Inability to carry out usual activities.
Grade 4 (Life-threatening or disabling )	Immediate risk of death.
Grade 5 (Fatal)	Resulting in death

Relationship of an AE or SAE to study medication is to be determined by the Investigator based on the definitions in Table 8. Relationship should be attributed not only to the combination regimen, but also to each drug within the combination regimen.

**Table 8: Adverse Event Relatedness**

Relationship to Product(s)	Definition
Not Related	No relationship between the event, including laboratory test abnormality and the administration of study drug. There is no temporal relationship and there is unambiguous evidence supporting another cause.
Unlikely Related	A clinical event, including laboratory test abnormality, with a temporal relationship to study drug administration which makes a causal relationship improbable, and in which other drugs/chemicals or underlying disease provide plausible explanations.
Possibly Related	A clinical event, including laboratory test abnormality with a reasonable time sequence to administration of study drug, but which could also be explained by concurrent disease or other drugs or chemicals.
Probably Related	A clinical event, including laboratory test abnormality, with a reasonable time sequence to administration of study drug, unlikely to be attributed to concurrent disease or other drugs or chemicals and which follows a clinically reasonable response on withdrawal (de-challenge). Re-challenge information is not required to fulfill this definition. The association of the clinical event/laboratory abnormality must also have some biologic plausibility, at least on theoretical grounds.
Definitely Related	A clinical event, including laboratory test abnormality, occurring in a plausible time relationship to administration of study drug, and which cannot be explained by concurrent disease or other drugs or chemicals. The response to withdrawal of the drug (de-challenge) should be clinically plausible. The event must be definitive pharmacologically or phenomenologically, using a satisfactory re-challenge procedure if necessary.
NCI Guidelines for Investigators: Adverse Event Reporting Requirements for DCTD (CTEP and CIP) and DCP INDs and IDEs (effective September 16, 2013): http://ctep.cancer.gov/protocolDevelopment/electronic_applications/docs/aeguidelines.pdf	

## 9.2. Recording Adverse Events

### 9.2.1. Reporting Serious Adverse Events

Any SAE, regardless of relationship to study medication, which occurs in a patient from the time informed consent is obtained until 30 days after the last study treatment, should be recorded by the clinical site on an SAE Report form. This reporting requirement also includes SAEs that are attributed to a study procedure performed during the screening period (from the time of consent until the time of first dose of study treatment). The SAE must be completely described on the patient's eCRF, including the judgment of the Investigator as to the relationship of the SAE to the study treatment (Debio 1562 and rituximab). The Investigator will promptly supply all information identified and requested by the Sponsor (or Contract Research Organization [CRO]) regarding the SAE.

The Investigator must report the SAE to the Sponsor's Medical Director or designee. The SAE Report form must be completed and submitted within 24 hours of the Investigator's learning of the event to the contact persons listed in the Study Manual provided to each site and maintained in the Investigator study files. Any follow-up information must also be completed on an SAE Report form and submitted to the same contacts.

When reporting SAEs, the following additional points should be noted:

- The underlying diagnosis or syndrome should be reported as the primary SAE term, rather than the signs or symptoms (signs and symptoms may be described in the narrative).
- Progression of disease should not be reported as an SAE; any serious medical event/condition that results from progression of underlying disease should be reported as the SAE.
- Death should not be reported as an SAE, but rather as an outcome of a specific SAE, unless the event preceding the death is unknown. In these exceptional cases, death may be used as an event term. If an autopsy was performed, the autopsy report should be provided.

It is the responsibility of the Sponsor to ensure that each Investigator receives a copy of any Council for International Organizations of Medical Sciences (CIOMS) or MedWatch report that has been submitted to the appropriate national regulatory agencies as notification of a suspected unexpected serious adverse reaction (SUSAR). The Investigator (or Sponsor or Sponsor's representative if so designated) must promptly report all SUSARs to the Institutional Review Board (IRB)/Independent Ethics Committee (IEC) for review in accordance with national regulations. IRB/IEC notification of the SUSAR may take the form of a submission of a copy of the CIOMS/MedWatch report or other format accepted by the IRB/IEC. A copy of the CIOMS/MedWatch report and notification to IRB/IEC should be retained in the site's study files.

In addition to CIOMS/MedWatch reports, the Sponsor will also notify the Investigators and IRBs/IECs of all deaths that occur during the study, irrespective of relationship to study medication, through annual updates to the Debio 1562 IB.

Disease progression and/or progression of the disease under study are anticipated occurrences in oncology drug development, and as such, are considered expected as per the current IB for the

compound. If a patient expires from progression of disease and/or from the disease under study during the period of obligation to report SAEs, disease progression and/or progression of the disease under study with a fatal outcome do not need to be reported as SAEs. The applicable protocol eCRF page(s) pertaining to death should be appropriately completed however, as disease progression.

#### **9.2.2. Reporting a Pregnancy**

Pregnancy and lactation are exclusion criteria. The Sponsor must be notified in the event of a pregnancy, reported by a patient or patient's partner, during the course of the study and through 30 days after the patient's last dose of Debio 1562. Pregnancy is not to be reported as an AE. However, SAEs associated with or resulting from the pregnancy should be recorded, and the pregnancy reporting form should be used to report the pregnancy. The pregnancy will be followed through delivery or final outcome.

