All patients will be contacted every 12 weeks ( $\pm$  4 weeks) from the time of the 30-day safety follow-up visit until one year from last patient's first study treatment.

**Statistical methods:** All statistical analyses will be performed using the most recently released and available Statistical Analysis Software (SAS) statistical software, unless otherwise noted. For categorical variables, the number and percent of each category within a parameter will be calculated. For continuous variables, the sample size (n), mean, median, and standard deviation, as well as the minimum and maximum values, will be presented. Missing data will not be imputed unless otherwise stated. There will be a summary of patient disposition, patient demographics, and baseline characteristics. PK parameters will be computed and presented in tables and listings. Plasma concentrations will be presented in graphs for each patient and by cohorts. Latest version of SAS or WinNonlin will be used for the PK analyses.

No formal interim analysis for efficacy will be performed; however, futility analyses will be conducted after 10 patients and, if deemed necessary, 15 patients in cohort A are evaluable for efficacy (i.e., patients should have performed at least one post baseline objective response assessment- *unless there is earlier clear evidence of PD*), as well as cumulative after enrollment of every 10 evaluable patients for efficacy (if deemed necessary) in study Part 3. At each analysis, futility will be evaluated using a Bayesian approach with a non-informative conjugate prior. The decision rule will be to recommend stopping for futility if there is sufficiently low probability (20% or less) that Objective Response Rate (ORR) exceeds the pre-specified (historical) control response of 40%. The primary analysis will be conducted after all enrolled patients reached their 3rd on-treatment scheduled response assessment or have discontinued from treatment. The final analysis will be triggered one year after the last accrued patient's first dose date. In the exceptional

case that after the final analysis a patient(s) might continue to receive study treatment under the protocol, any subsequent data generated from this patient(s) will be summarized in an addendum report to be issued after the last treatment of the last patient.

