  - Serum creatinine  $\leq 2.0 \times$  upper limit of normal (ULN) or 24-hour creatinine clearance of  $\geq 60$  mL/minute
  - AST  $\leq 2.5 \times$  ULN; ALT  $\leq 2.5 \times$  ULN and

- Total bilirubin  $\leq 1.5 \times$  ULN; patients with documented diagnosis of Gilbert syndrome are eligible if total bilirubin  $\leq 3.0 \times$  ULN.

7) Patients must have evaluable or measurable disease in accordance with the International Working Group Guidelines for Lymphoma ([Cheson 2014](#)).

8) Patients who are Hepatitis B surface antigen (HBsAg) + (must be polymerase chain reaction [PCR] negative) who are taking antivirals are allowed to enroll.

9) Male patients and female patients of child bearing potential participating in this study must agree to use two highly effective methods of contraception throughout the study and for at least 12 weeks after the last dose of Debio 1562 and 12 months after the last dose of rituximab. Examples of acceptable birth control methods include but are not limited to the following methods: (e.g., oral, parenteral, or implantable hormonal contraceptive; tubal ligation; intra-uterine device; barrier contraceptive with spermicide; partner's latex condom or vasectomy).

10) Patients must be willing to provide informed consent and be willing to comply with the study protocol.

11) Patients must have available a pathology-informed fresh or archived tumor tissue biopsy reflecting the current DLBCL disease. If the tissue biopsy is older than 18 months from the screening visit and a fresh one cannot be available, patients should provide fine needle aspiration (FNA) samples.

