**Figure 5: Schematic Overview of the Study Design**

### Study treatment duration

Patients will receive study treatment for six 21-day cycles, or until they develop unacceptable toxicity, withdraw consent, or the Sponsor terminates the study. Permission to prolong the study treatment could be exceptionally granted by Study Sponsor if patients are deriving benefit from the study treatment and after complete presentation of the individual case by the Study Investigator, particularly the medical justification for extending the treatment and the re-assessment of the risk/benefit balance. The Sponsor's decision will consider the availability of investigational medicinal product (IMP) at the time of the request. A report of the discussions with the Sponsor must be filed in the source documentation.

Patients who display intolerance to the combination regimen may be eligible to continue treatment with single agent Debio 1562.

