#### **5.7.4.2. Rituximab**

Rituximab will be administered at a dose of  $375 \text{ mg/m}^2$  at Day 1 of each 21-day cycle, after administration of Debio 1562 (no minimum time-interval is required between finishing Debio 1562 and starting rituximab), throughout the study as follows:

- Dose 1 (Cycle 1, Day 1): infusion will be initiated at a rate of 50 mg/h and if tolerated, the rate will be increased in increments of 50 mg/h every 30 minutes up to a maximum of 400 mg/h.
- For subsequent doses, the infusion will begin at a rate of 100 mg/h and, if tolerated, the rate will be increased in increments of 100 mg/h every 30 minutes up to 400 mg/h.

Rituximab will be infused over approximately four hours.

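### The explicit post-dose limit on pregnancy notification (30 days, Debio 1562 only) is shorter than both contraception periods, so it is unclear whether later pregnancies must be reported

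*Protocol*

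**What the plan says.** Three places in the protocol bear on this.

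- **Section 9.2.2, Reporting a Pregnancy.** The sponsor must be told of a pregnancy in a patient or a patient's partner "during the course of the study and through 30 days after the patient's last dose of Debio 1562". A notified pregnancy is followed to its outcome. The only stated post-dose limit is "through 30 days after the patient's last dose of Debio 1562"; rituximab is not mentioned.
- **Section 3.1, inclusion criterion 9.** Male patients and female patients of child-bearing potential must agree to contraceptive measures "throughout the study and for at least 12 weeks after the last dose of Debio 1562 and 12 months after the last dose of rituximab".
- **Section 8.11, Pregnancy Screen.** "If a female patient becomes pregnant while participating in this study, the Investigator and Sponsor must be informed immediately". This rule has no 30-day limit, does not mention partners, and cross-refers to Section 9.2.2.

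After the 30-day safety visit, patients are contacted every 12 weeks "until one year from last patient's first study treatment" (Synopsis, treatment and study duration). Section 5.10.1 requires no clinic visit for survival follow-up, and nothing says that pregnancy is asked about at these contacts. Scheduled pregnancy tests end at the 30-day visit (Appendices A to C).

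**The concern.** Criterion 9 asks patients to avoid conception well beyond day 30, and its longer period is tied to rituximab. The only post-dose limit stated for notification is 30 days and is tied to Debio 1562 alone. By contrast, the SAE window in Section 9.2.1 runs from the last study treatment.

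What is at stake is the capture of fetal outcomes. A congenital anomaly is an SAE criterion (Section 9.1.1.2), but SAE recording generally ends 30 days after the last study treatment. Follow-up of a notified pregnancy under Section 9.2.2 is therefore the main route to a fetal outcome. A pregnancy that need not be notified need not be followed.

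**Working it through.** The plan states no coverage figure to reproduce, so the check compares time windows.

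**Inputs**
- Contraception (criterion 9): 12 × 7 = 84 days after the last Debio 1562 dose; 12 months, taken as 365 days, after the last rituximab dose.
- Explicit post-dose notification limit (Section 9.2.2): 30 days after the last Debio 1562 dose.
- Treatment length (Section 4.1.1): "Patients will receive study treatment for six 21-day cycles", so the last Day 1 falls (6 − 1) × 21 = 105 days after the first dose.
- Rituximab timing (Section 5.7.4.2): "at Day 1 of each 21-day cycle, after administration of Debio 1562". On Q3W both last doses fall on the same day. On QW the last Debio 1562 dose (Day 15) is 14 days after the last rituximab dose.
- End of study (Section 11.10): the later of the safety visit of the last patient on treatment and one year from the last accrued patient's first visit.

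**Reading 1: notification stops 30 days after Debio 1562**
- After Debio 1562: 30/84 = 36% covered; 84 − 30 = 54 days outside.
- After rituximab, Q3W: 30/365 = 8% covered; 365 − 30 = 335 days outside.
- After rituximab, QW: (14 + 30)/365 = 44/365 = 12% covered; 365 − 44 = 321 days outside.

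**Reading 2: the course of the study runs to end of study**

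Take the last-accrued patient, with six cycles and with first visit equal to first dose. The study then reaches day 365.
- The Debio 1562 period ends at day 105 + 84 = 189 (Q3W) or 105 + 14 + 84 = 203 (QW). Both fall before day 365, so all 84 days are covered.
- The rituximab period ends at day 105 + 365 = 470. Covered: 365 − 105 = 260 days, and 260/365 = 71%. Outside: 470 − 365 = 105 days.
- A six-cycle patient who started at least 105 days before the last-accrued patient is fully covered.
- If the first visit is instead a screening visit up to 28 days before the first dose, cover falls to as little as 260 − 28 = 232 days, and 232/365 = 64%.
- If a patient on extended treatment finishes after the one-year point, end of study is that patient's safety visit, scheduled at 30 to 42 days. For that patient the two readings nearly coincide.

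**Section 8.11.** On either reading of Section 9.2.2, a female patient still in follow-up is arguably covered. A partner is not.

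**The case against.** The strongest reply is that notification does not end at day 30. Section 9.2.2 joins the course of the study and the 30 days with *and*, which can be read as additive. The study includes a follow-up period (Section 4.1.1), and Section 5.10 separates stopping treatment from leaving the study. Section 8.11 requires immediate notification for female participants with no day limit. A contraception commitment and a reporting window also serve different purposes, and 30 days matches the AE and SAE windows. Section 9.1 gives a route for drug-related events after the end of study.

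Much of this stands. The 30-day stop is one reading of an ambiguous sentence, so the 36%, 8% and 12% are conditional on it. A shorter reporting window is not in itself a contradiction.

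It does not remove the point, for four reasons. First, if follow-up is already included, the 30-day clause adds little for a patient who stays in the study, because the study cannot end before the last treated patient's safety visit. That makes the restrictive reading a natural one for a site to adopt. Second, the additive reading still leaves late-accrued and extended-treatment patients short after rituximab. Third, Section 8.11 omits partners. Fourth, the Section 9.1 route is at the investigator's discretion and concerns AEs, whereas Section 9.2.2 says a pregnancy is not reported as an AE.

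A reader might go further and infer that most pregnancies in the risk period would go unreported. The documents do not support that. They give neither a pregnancy rate nor the number of patients of child-bearing potential, and a share of days is not a share of pregnancies, particularly when two contraceptive methods are required.

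**Conclusion.** The point holds as a mismatch with an unclear end date. Post-rituximab cover ranges from 8% (Q3W) or 12% (QW) on the restrictive reading to about 71% for the last-accrued six-cycle patient on the broad one, and to 100% for six-cycle patients who started at least 105 days earlier. Post-Debio 1562 cover is 36% or 100% for a six-cycle patient. Partner pregnancies are the most exposed.

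The figures assume six full cycles of both drugs without delays or skipped doses, 12 months equal to 365 days, and, for the 71%, first visit equal to first dose. A patient who stops rituximab early and continues Debio 1562 alone would have more of the post-rituximab period covered.

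This is a patient-safety reporting point and touches no efficacy endpoint or analysis. Enrollment was complete by Amendment 6, but Section 1.9 records three patients still on QW treatment on April 14, 2020, so their post-dose periods were still to come.

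**What to change.** Reconcile Section 9.2.2, Section 8.11 and inclusion criterion 9. State one notification period for patients and partners, with an end date anchored to the last dose of each drug and consistent with the contraception periods the protocol already requires. Add a pregnancy question to the existing 12-weekly contacts while they last, and instruct patients to report a pregnancy to the site after that. No dose, treatment or contraception rule needs to change.

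Measured against a 30-day stop, alignment adds 54 days after Debio 1562 and 335 (Q3W) or 321 (QW) days after rituximab. Measured against the broad reading, it adds about 105 days for the last-accrued six-cycle patient.

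The cost is a short text change and no extra visit. The downside is a somewhat longer passive reporting duty for late-accrued or extended-treatment patients, because the scheduled contacts end one year from the last patient's first treatment, before those patients' post-rituximab period does.
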